8.1.5 Electrocardiogram (ECG)

A 12-lead ECG will be assessed using a standard ECG machine according to local procedures at the time points shown in Table 1.

Heart rate, QRS, PR and QT intervals will be recorded from the ECGs. The ECGs will be interpreted and signed and dated by the investigator or his/her designee.

The QT interval by be corrected using Fridericia's formula (QTcF) will be added to the summary tables as described below.

Continuous values of ECG will be summarized by parameter and visit including change from baseline.

8.1.6 Laboratory Safety Data

Laboratory safety parameters are listed described in Table 2. All results will be recorded in the eCRF and will be assessed as clinically significant or not clinically significant. Since local laboratories are used laboratory parameters will be converted to units as indicated in Table 2 before summarizing.

Table 2 Laboratory safety parameters

Category	Laboratory Parameter (unit)
Haematology	Haemoglobin (g/dL), RBC (10 ¹² /L) Red Blood Cell Distribution Width (RDW) (%) Haematocrit (%) Mean cell volume (MCV) (fL) Mean cell haemoglobin (MCH) (pg) Mean cell haemoglobin concentration (MCHC) (g/dL) Platelet count (10 ⁹ /L) WBC and differential counts (absolute and percentage): Neutrophils (% and 10 ⁹ /L) Lymphocytes (% and 10 ⁹ /L) Monocytes (% and 10 ⁹ /L) Eosinophils (% and 10 ⁹ /L) Basophils (% and 10 ⁹ /L) Prothrombin Time International Normalised Ratio (PT-INR)
Clinical chemistry	Aspartate Aminotransferase (AST) (U/L) Alanine Aminotransferase (ALT) (U/L) Gamma Glutamyl Transpeptidase (GGT) (U/L) Alkaline Phosphatase (U/L) Bilirubin (mg/dL) Urea (mg/dL) S-Creatinine (mg/dL) Potassium (mmol/L) Sodium (mmol/L) Calcium (mg/dL) Chloride (mmol/L) Phosphate (mg/dL) Total protein (g/dL) Albumin (g/dL) C-Reactive Protein (CRP) (mg/dL) Glucose (non-fasting) (mg/dL)

Laboratory safety data will be summarized using descriptive statistics, including means, medians, SDs, and minimum and maximum by time point and treatment, including changes from baseline. In addition, laboratory safety data will be plotted using boxplots by time point and treatment.

A mean and CI plot over time will be presented for haemoglobin as well as for change from baseline in haemoglobin.

Abnormal values will be listed by subject, visit and safety parameter.

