Pre-clinical studies in cynomolgus monkeys show that molgramostim nebuliser solution is well tolerated locally and that it has low systemic toxicity. The small fraction of the inhaled dose that is absorbed systemically causes increases in stem cell proliferation, resulting in increased number of monocytes, eosinophils and neutrophils in the circulation; similar to the known effects after intravenous administration of rhGM-CSF. Local effects in the lungs are characterised by accumulation of inflammatory cells, mostly macrophages, accompanied by an increased cellularity in the lymphoid tissue that is associated with the respiratory tract and minimal to mild exudation of red blood cells (RBC) into the alveoli. The infiltration of inflammatory cells was not associated with any signs of inflammation or impaired lung function, and it is interpreted as an exaggerated pharmacological effect of molgramostim. Its severity was graded slight at the 10 µg/kg/day dose level and moderate above this level. Duration of treatment did not affect the severity of this finding. Reduced severity of the lung and tracheobronchial changes following 4 weeks off dose in recovery animals suggests partial resolution of the changes.

An embryo-foetal developmental (EFD) toxicity trial in rabbits revealed increases in post implantation loss, decreases in the number of live implants, effects on sex ratio and a slight increase in the incidence of major malformations in foetuses at the highest dose (150 µg/kg/day). Studies in sexually mature monkeys have shown that molgramostim has no effect on male and female reproductive organs. Further details are available in the IB. The nonclinical data raises a concern about human teratogenicity/fetotoxicity in early pregnancy, risk mitigation measures (contraception and pregnancy testing) have therefore been implemented in the trial.

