Changes in white blood cells (WBC) and differential counts were in line with the mode-of-action of GM-CSF and these were not clinically significant in most subjects. In subjects treated with molgramostim nebuliser solution a slight increase in total WBC and differential counts (primarily within normal reference ranges) was observed in a dose-dependent manner. Two subjects had adverse events (AEs) concerning WBC differential counts that were considered related to GM-CSF (eosinophilia and white blood cell count increased).

The most common AE was cough, reported for 21/30 (70%) subjects receiving molgramostim nebuliser solution and 8/12 (67%) receiving placebo. The AEs considered treatment-related reported by two or more (>5%) subjects receiving molgramostim nebuliser solution were: cough (50%), productive cough (10%) and headache (6.7%). Cough was considered treatment-related for a similar proportion of subjects receiving placebo (58%). Number of cough events was 48 in 30 subjects in the combined molgramostim groups and 15 in 12 subjects in the placebo groups. A higher number of treatment-related AEs were observed in the 600 µg dose level compared to the 300 µg dose level and placebo in the MAD part. There was no development of anti-drug antibodies up to 28 days after last dose. There were no serious adverse events (SAEs), severe AEs, dose-limiting toxicity, or other remarkable findings of clinical concern from review of clinical safety data. Further details are available in the IB.

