Based on information from similar products, the potential dose-limiting toxicity of molgramostim would be based on pulmonary effects, such as bronchoconstriction, dyspnoea, cough or decreased pulmonary function. Pulmonary function and respiratory symptoms will be monitored during the trial and treatment should be discontinued if significant worsening occurs. If there is significant systemic exposure, haematologic findings such as leukocytosis and neutrophilia may occur. As non-clinical data indicate that systemic exposure to rhGM-CSF may be associated with increased pre- and post-implantation losses, pregnancy testing will be performed in women of childbearing potential at each trial visit where molgramostim is dispensed and at home at monthly intervals during treatment.

Treatment with molgramostim nebuliser solution is expected to be more effective, less invasive, and more convenient, than the currently available symptomatic treatment, WLL, for patients with aPAP.

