10.9.2.5. Abnormal Laboratory Values/Vital Signs

An asymptomatic abnormal laboratory/vital sign finding should only be reported as an AE if it is clinically significant according to the investigator's assessment, if it fulfils the criteria for an SAE or if it causes the subject to discontinue the trial.

If an abnormal laboratory/vital sign value is associated with clinical signs and symptoms, the sign/symptom should be reported as an AE and the associated laboratory/vital sign result should be considered additional information.

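### Apart from events reported as AEs, no planned table counts the subjects with abnormally high white-cell, neutrophil, eosinophil or monocyte counts

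*SAP*

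**What the plan says.** **The effect.** Protocol 4.3 states that, given significant systemic exposure, "haematologic findings such as leukocytosis and neutrophilia may occur". Protocol 10.9.3.4 repeats this for overdose. Protocol 4.1 describes stem-cell proliferation in monkeys "resulting in increased number of monocytes, eosinophils and neutrophils in the circulation". For phase I it reports a dose-dependent rise in white cells and differential counts, and two subjects with AEs considered related to GM-CSF: one eosinophilia, one raised white-cell count.

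**The planned output.** SAP 8.1.6 treats all laboratory parameters alike: "Laboratory safety data will be summarized using descriptive statistics, including means, medians, SDs, and minimum and maximum by time point and treatment". The same section also plans summaries of change since baseline, and boxplots for each visit and arm. Abnormal values are listed by subject, visit and parameter. SAP Section 13 contains two haematology tables, 14.3.4.1 (values) and 14.3.4.2 (change from baseline). Results come from local laboratories; SAP 8.1.6 converts units and says nothing about harmonising reference ranges.

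**The AE route.** Protocol 10.8.5 requires clinically significant findings that are new since Baseline to be reported as AEs. Protocol 10.9.2.5 limits this: "An asymptomatic abnormal laboratory/vital sign finding should only be reported as an AE if it is clinically significant" in the investigator's assessment, or if it is serious or causes the subject to discontinue the trial. SAP 8.1.2 restricts the safety summaries to treatment-emergent events.

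**The concern.** The natural question about a haematopoietic growth factor given for up to 36 months is how many treated subjects developed raised counts. That is a count of distinct subjects over follow-up. The planned tables describe the distribution of values at one visit at a time, pooled over laboratories that may use different ranges.

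The AE tables answer a narrower question, because they depend on an investigator's judgement of clinical significance. Protocol 4.1 says of the phase I changes that "these were not clinically significant in most subjects". A subject with an asymptomatic count above range that was not judged significant would therefore appear in the listing and in no count.

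The matter is more than presentation. SAP 3.2 says these data will contribute to the risk-benefit profile and to a possible future marketing application. GM-CSF levels are sampled only in Italy, and SAP 7.3 only lists the quantifiable ones, so blood counts are the main systemic readout for the whole cohort.

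**Working it through.** The plan states no figure to reproduce. The check has two parts.

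**1. Is there a count anywhere?** Each output in SAP Sections 12 to 14 that bears on haematology, set against the question of how many subjects had a high count:

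| Output | What it gives | Counts subjects with high values? |
|---|---|---|
| Table 14.3.4.1 | values by visit | no |
| Table 14.3.4.2 | change by visit | no |
| Boxplots (SAP 8.1.6) | distribution by visit | no |
| Listing 16.2.8.1 | individual data | only by hand |
| Tables 14.3.1.x | treatment-emergent AEs by preferred term | yes, for the subset reported as AEs |

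There is no shift table and no count above the upper limit. The clinical-significance assessment recorded for every result is not tabulated either, although Protocol Section 11 presents categorical data as counts and percentages.

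**2. Can the number be recovered from the by-visit statistics?** Inputs: n = 55, the number on active treatment at termination (SAP 3.2), used here as an assumed safety-set size; 60, all enrolled, is the upper end. Six post-baseline visits (Visits 2 to 7). Assumed for illustration only: all subjects attend every visit, an affected subject shows a rise of 1.5 x 10^9/L, and the others do not change. Intervals are exact (Clopper-Pearson), 95%, two-sided.

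*Same tables, different incidence.*
- Case A: one subject is high at all six visits.
- Case B: six different subjects are each high at one visit, one per visit.
- In both cases each visit has exactly one subject up by 1.5. Mean change = 1.5/55 = 0.027, median 0, minimum 0, maximum 1.5, and the SD is the same. The change tables are identical.
- Incidence in A = 1/55 = 1.8% (0.05% to 9.7%). Incidence in B = 6/55 = 10.9% (4.1% to 22.2%).
- With n = 60: 1.7% (0.04% to 8.9%) against 10.0% (3.8% to 20.5%).

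*Dilution at a single visit.* If 5 of 55 are high together:
- mean change = 5 x 1.5/55 = 0.14; median 0; maximum 1.5
- SD = 1.5 x sqrt[(5/55)(50/55)(55/54)] = 0.44
- incidence = 9.1% (3.0% to 20.0%)
- with n = 60: mean 0.125; incidence 8.3% (2.8% to 18.4%)

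The maximum and SD would alert a careful reader to outliers but would not say how many subjects were above range.

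*A null result is also informative.* No affected subjects gives an upper limit of 6.5% (0/55) or 6.0% (0/60).

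**The case against.** The strongest case against has several parts.

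- **Counts are not wholly absent.** A reader might infer that raised counts are tabulated nowhere. The documents do not support that: new, treatment-emergent findings judged clinically significant are counted by preferred term, with number and proportion of subjects. This stands. The gap is the remainder: asymptomatic values above range that were not judged significant.
- **The summaries go beyond means.** Medians, SDs, ranges and boxplots are planned, and with 60 enrolled subjects someone could count from the listing. This stands as far as it goes, but a hand count from a listing gives no prespecified denominator, percentage or comparison with baseline. Part 2 of the working shows that the by-visit statistics cannot replace it.
- **The risk is qualified.** Protocol 4.3 makes it conditional on significant systemic exposure. Protocol 4.1 reports picogram-level absorption and phase I rises mostly inside the normal range. Protocol 10.9.3.3 names no AEs of special interest. This stands and lowers the expected incidence. A count would show whether the same holds over long-term use.
- **Reference ranges may not be available.** Neither document says that local ranges are captured in the eCRF, or defines abnormal for the listing. This stands and is carried into the fix. The planned listing of abnormal values nevertheless needs some such classification.
- **Haemoglobin.** Of the plots, SAP 8.1.6 says: "A mean and CI plot over time will be presented for haemoglobin". A reader might infer that this plot is misplaced, since no haemoglobin risk is stated. That is preference, not error: haemoglobin enters the DLCO correction in SAP 7.2.5, and the plot takes nothing from white-cell reporting.
- **Unscheduled samples.** One might infer that they are excluded from the summaries. SAP 8.1.6 does not say so; it is silent on where they go.

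**Conclusion.** The point holds in a limited form. For four parameters tied to the drug's known pharmacology, the plan tabulates by-visit distributions and a judgement-filtered set of AEs. It does not tabulate the number of subjects whose counts went above range. In the illustration, identical by-visit change tables are compatible with incidences of 1.8% and 10.9%. Those figures rest on the assumed rise, complete attendance and a safety set of 55. The true safety set is everyone exposed within the trial, and using 60 changes the figures little. That by-visit statistics do not determine the number of distinct subjects affected does not depend on these values.

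A reader might go further and infer that a planned result is wrong or biased, or that the trial would miss clinically important leukocytosis. The documents support neither: every planned figure is valid for what it describes, and findings judged clinically significant are reported as AEs. This is a worthwhile, inexpensive addition to a descriptive safety plan.

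**What to change.** In SAP 8.1.6 and table Section 14.3.4, add for WBC, neutrophils, eosinophils and monocytes, on the safety analysis set and with the column layout of SAP 5.1:

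1. A shift table from the baseline category to the category of the highest on-treatment value, using scheduled and unscheduled samples. State the on-treatment window.
2. The number and percentage of subjects with any post-baseline value above range. The denominator should be subjects with at least one post-baseline result.

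Use the same abnormality classification as the planned listing, and write it into SAP 8.1.6. If local ranges were not captured, state one common threshold per parameter and apply it to the converted units. Keep the haemoglobin plot.

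The cost is a few extra descriptive tables, some of them showing expected and benign rises. There may also be work to obtain local ranges after treatment has ended, since this SAP version dates from January 2021 and treatment was to run until the end of 2020.

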8.1.7 CT Scans

A CT scan is not required as part of this trial. Only if a CT scan is performed according to clinical practice or medical need, e.g. in case of a clinical deterioration, the results will be recorded in the eCRF as improved / worsened / no change / data missing or impossible to evaluate, compared to the last evaluation in IMPALA.

Results of the CT scans will be listed by subject and visit.

8.2 Safety Update

A safety update will be performed with a planned data cutoff 1-February 2019.

The output generated for the safety update is listed below. For the output in section 14.2.4 (Whole lung lavage) the date of the cutoff will be used to calculate subject years.

- Table 14.1.1, 14.1.3, 14.1.5, 14.1.6
- Tables 14.2.4.1, 14.2.4.3
- Table 14.2.6.1
- All output in section 14.3
- Listing 16.2.6.4

9 Deviations from Protocol

A safety analysis set has been added. At the time of protocol generation all patients were expected to be treated from the beginning of this trial. Since some patients are not treated in this trial it was decided to include a safety analysis set

The secondary endpoint “time off treatment after discontinuation of inhaled molgramostim” is not reported due to insufficient data collection.

10 Software

All statistical calculations described in this SAP will be done by BioStata Aps using SAS, release 9.4 or later (SAS Institute, Cary, NC, USA).

11 Reference List

St George's respiratory questionnaire manual version 2.3, 2019, Paul Jones

12 List of Listings

- Listing 16.2.1.1 Violations of inclusion and/or exclusion criteria – screening failures
- Listing 16.2.1.2 Individual subject disposition (all subjects)
- Listing 16.2.1.3 Reason for withdrawal from trial (all subjects)
- Listing 16.2.2.1 Protocol deviations (all subjects)
- Listing 16.2.4.1 Individual subject demographics and baseline characteristics (all subjects)
- Listing 16.2.4.2 Individual medical history (all subjects)
- Listing 16.2.4.3 Individual concomitant medication (all subjects)
- Listing 16.2.4.4 COVID-19 positive subjects (all subjects)
- Listing 16.2.4.5 Adverse events occurring in COVID-19 positive subjects (all subjects)
- Listing 16.2.4.6 Protocol deviations due to COVID-19 (all subjects)
- Listing 16.2.5.1 Individual subject exposure (all subjects)
- Listing 16.2.5.2 Individual subject relative exposure (all subjects)
- Listing 16.2.5.3 Individual visits attended (all subjects)
- Listing 16.2.6.1 Individual (A-a)DO₂ (all subjects)
- Listing 16.2.6.2 Individual 6-minute walk test (all subjects)
- Listing 16.2.6.3 Individual St Georges respiratory questionnaire scores (all subjects)
- Listing 16.2.6.4 Individual whole lung lavage (all subjects)
- Listing 16.2.6.5 Individual lung function tests (all subjects)
- Listing 16.2.6.6 Individual disease severity scores (all subjects)
- Listing 16.2.6.7 Subjects with oxygen supplement during trial (all subjects)
- Listing 16.2.6.8 Individual overall clinical assessments (all subjects)
- Listing 16.2.6.9 Individual GM-CSF measurements above lower level of quantification (all subjects)
- Listing 16.2.7.1 Adverse events (all subjects)
- Listing 16.2.7.2 Serious adverse events (all subjects)

Listing 16.2.7.3 Adverse drug reactions (all subjects)

Listing 16.2.7.4 Adverse events leading to treatment discontinuation (all subjects)

Listing 16.2.8.1 Individual haematology (all subjects)

Listing 16.2.8.2 Individual clinical chemistry (all subjects)

Listing 16.2.9.1 Individual vital signs (all subjects)

Listing 16.2.9.2 Individual electrocardiogram (all subjects)

Listing 16.2.10.1 Individual CT scans (all subjects)

13 List of Tables

Section 14.1

Table 14.1.1 Subject disposition (full analysis set)

Table 14.1.2 Number of subjects by visit (full analysis set)

Table 14.1.3 Baseline demographics (full analysis set)

Table 14.1.4 Medical history (full analysis set)

Table 14.1.5 Summary of exposure (months) (safety analysis set)

Table 14.1.6 Summary of cumulative exposure (safety analysis set)

Table 14.1.7 Summary of relative exposure (safety analysis set)

Table 14.1.8 Summary of last visit attended (full analysis set)

Table 14.1.9 Concomitant medication (safety analysis set)

Table 14.1.10. Summary of missed key secondary endpoints assessments due to COVID-19 pandemic (safety analysis set)

Table 14.1.11 Summary of alternative endpoint ascertainment due to COVID-19 pandemic (safety analysis set)

Section 14.2

(14.2.1: Blood gas analysis endpoints)

Table 14.2.1.1 Summary of (A-a)DO₂ (mmHg) (full analysis set)

Table 14.2.1.2 Summary of change from baseline in (A-a)DO₂ (mmHg) (full analysis set)

(14.2.2: 6 minutes walking test endpoints)

Table 14.2.2.1 Summary of 6 minutes walking distance (m) (full analysis set)

Table 14.2.2.2 Summary of change from baseline in 6 minutes walking distance (m) (full analysis set)

Table 14.2.2.3 Summary of pre-walk dyspnoea score (Borg CR10) (full analysis set)

Table 14.2.2.4 Summary of change from baseline in 6 minutes walking distance (m) (full analysis set)

Table 14.2.2.5 Summary of post-walk dyspnoea score (Borg CR10) (full analysis set)

Table 14.2.2.6 Summary of change from baseline in dyspnoea score (Borg CR10) (full analysis set)

Table 14.2.2.7 Summary of SpO₂ at start of walk (%) (full analysis set)

Table 14.2.2.8 Summary of change from baseline in SpO₂ at start of walk (%) (full analysis set)

Table 14.2.2.9 Summary of worst SpO₂ during walk (%) (full analysis set)

Table 14.2.2.10 Summary of change from baseline in worst SpO₂ during walk (%) (full analysis set)

Table 14.2.2.11 Summary of desaturation during walk (%) (full analysis set)

Table 14.2.2.12 Summary of change from baseline in desaturation during walk (%) (full analysis set)

Table 14.2.2.13 Summary of completion of 6 minutes walking test (full analysis set)

(14.2.3: SGRQ endpoints)

Table 14.2.3.1 Summary of SGRQ total score (full analysis set)

Table 14.2.3.2 Summary of change from baseline in SGRQ total score (full analysis set)

Table 14.2.3.3 Summary of SGRQ symptoms score (full analysis set)

Table 14.2.3.4 Summary of change from baseline in SGRQ symptoms score (full analysis set)

Table 14.2.3.5 Summary of SGRQ activity score (full analysis set)

Table 14.2.3.6 Summary of change from baseline in SGRQ activity score (full analysis set)

Table 14.2.3.7 Summary of SGRQ impact score (full analysis set)

Table 14.2.3.8 Summary of change from baseline in SGRQ impact score (full analysis set)

(14.2.4: Whole lung lavage endpoints)

Table 14.2.4.1 Summary of number of subjects with a whole lung lavage between IMPALA and IMPALA-Z (safety analysis set)

Table 14.2.4.2 Summary of whole lung lavage (safety analysis set)

Table 14.2.4.3 Summary of whole lung lavage by location (safety analysis set)

Table 14.2.4.4 Summary of volume of saline used during whole lung lavage (L) (safety analysis set)

(14.2.5: Lung function test endpoints)

Table 14.2.5.1 Summary of DLCO (%) (full analysis set)

Table 14.2.5.2 Summary of change from baseline in DLCO (%) (full analysis set)

Table 14.2.5.3 Summary of FEV1 (%) (full analysis set)

Table 14.2.5.4 Summary of change from baseline in FEV1 (%) (full analysis set)

Table 14.2.5.5 Summary of FVC (%) (full analysis set)

Table 14.2.5.6 Summary of change from baseline in FVC (%) (full analysis set)

(14.2.6: Disease severity score)

Table 14.2.6.1 Summary of disease severity score (full analysis set)

Table 14.2.6.2 Summary of change in disease severity score compared to baseline (full analysis set)

(14.2.7: Supplemental oxygen during trial)

Table 14.2.7.1 Summary of oxygen supplement anytime during the trial (full analysis set)

Table 14.2.7.2: Summary of oxygen supplement ongoing at baseline (full analysis set)

Table 14.2.7.3: Summary of oxygen supplement ongoing at end of trial (full analysis set)

Table 14.2.7.4: Summary of oxygen supplement ongoing at baseline and ongoing at end of trial (full analysis set)

Table 14.2.7.5: Summary of oxygen supplement started after baseline and stopped before end of trial (full analysis set)

(14.2.8: Overall clinical assessment)

Table 14.2.8.1 Summary of status of aPAP (full analysis set)

Table 14.2.8.2 Summary of requirement for treatment since last visit (full analysis set)

Section 14.3

(14.3.1: Adverse events)

Table 14.3.1.1 Overview of adverse events (safety analysis set)

Table 14.3.1.2 Summary of treatment emergent adverse events by SOC and preferred term (safety analysis set)

Table 14.3.1.3 Summary of treatment emergent adverse events by preferred term - frequency \geq 5% (safety analysis set)

Table 14.3.1.4 Summary of treatment emergent adverse events by severity and SOC and preferred term (safety analysis set)

Table 14.3.1.5 Summary of treatment emergent adverse events by relationship and SOC and preferred term (safety analysis set)

Table 14.3.1.6 Summary of treatment emergent adverse events by outcome and SOC and preferred term (safety analysis set)

Table 14.3.1.7 Summary of treatment emergent serious adverse events by SOC and preferred term (safety analysis set)

Table 14.3.1.8 Summary of treatment emergent serious adverse events by severity, SOC and preferred term (safety analysis set)

Table 14.3.1.9 Summary of treatment emergent serious adverse events by relationship, SOC and preferred term (safety analysis set)

Table 14.3.1.10 Summary of treatment emergent serious adverse events by outcome, SOC and preferred term (safety analysis set)

Table 14.3.1.11 Summary of treatment emergent non-serious adverse events by SOC and preferred term (safety analysis set)

Table 14.3.1.12 Summary of treatment emergent non-serious adverse events by preferred term - frequency \geq 5% (safety analysis set)

Table 14.3.1.13 Summary of treatment emergent non-serious adverse events by severity, SOC and preferred term (safety analysis set)

Table 14.3.1.14 Summary of treatment emergent non-serious adverse events by relationship, SOC and preferred term (safety analysis set)

Table 14.3.1.15 Summary of treatment emergent non-serious adverse events by outcome, SOC and preferred term (safety analysis set)

Table 14.3.1.16 Summary of treatment emergent adverse drug reactions by SOC and preferred term (safety analysis set)

Table 14.3.1.17 Summary of treatment emergent adverse drug reactions by severity, SOC and preferred term (safety analysis set)

Table 14.3.1.18 Summary of treatment emergent adverse drug reactions by relationship, SOC and preferred term (safety analysis set)

Table 14.3.1.19 Summary of treatment emergent adverse drug reactions by outcome, SOC and preferred term (safety analysis set)

Table 14.3.1.20 Summary of treatment emergent adverse events leading to treatment discontinuation by SOC and preferred term (safety analysis set)

Table 14.3.1.21 Summary of treatment emergent adverse events leading to treatment discontinuation by severity, SOC and preferred term (safety analysis set)

Table 14.3.1.22 Summary of treatment emergent adverse events leading to treatment discontinuation by relationship, SOC and preferred term (safety analysis set)

Table 14.3.1.23 Summary of treatment emergent adverse events leading to treatment discontinuation by outcome, SOC and preferred term (safety analysis set)

(14.3.2: Vital signs)

Table 14.3.2.1 Summary of vital signs (safety analysis set)

Table 14.3.2.2 Summary of change from baseline in vital signs (safety analysis set)

(14.3.3: ECG)

Table 14.3.3.1 Summary of electrocardiogram (ECG) (safety analysis set)

Table 14.3.3.2 Summary of change from baseline in electrocardiogram (ECG) (safety analysis set)

(14.3.4: Safety lab)

Table 14.3.4.1 Summary of hematology parameters (safety analysis set)

Table 14.3.4.2 Summary of change from baseline in hematology parameters (safety analysis set)

Table 14.3.4.3 Summary of clinical chemistry parameters (safety analysis set)

Table 14.3.4.4 Summary of change from baseline in clinical chemistry parameters (safety analysis set)

14 List of Figures

Section 14.2

(14.2.1: Blood gas analysis endpoints)

Figure 14.2.1.1 Mean plot of (A-a)DO₂ (mmHg) (full analysis set)

(14.2.2: 6 minutes walking test endpoints)

Figure 14.2.2.1 Mean plot of 6 minutes walking distance (m) (full analysis set)

Figure 14.2.2.2 Mean plot of pre-walk dyspnoea score (Borg CR10) (full analysis set)

Figure 14.2.2.3 Mean plot of post-walk dyspnoea score (Borg CR10) (full analysis set)

Figure 14.2.2.4 Mean plot of SpO₂ at start of walk (%) (full analysis set)

Figure 14.2.2.5 Mean plot of worst SpO₂ during walk (%) (full analysis set)

Figure 14.2.2.6 Mean plot of desaturation during walk (%) (full analysis set)

(14.2.3: SGRQ endpoints)

Figure 14.2.3.1 Mean plot of SGRQ total score (full analysis set)

Figure 14.2.3.2 Mean plot of SGRQ symptoms score (full analysis set)

Figure 14.2.3.3 Mean plot of SGRQ activity score (full analysis set)

Figure 14.2.3.4 Mean plot of SGRQ impact score (full analysis set)

Section 14.3

(14.3.1: safety lab)

Figure 14.3.1.1 Mean plot of haemoglobin (mg/dL) (safety analysis set)

Figure 14.3.1.2 Mean plot of change from baseline in haemoglobin (mg/dL) (safety analysis set)
